UC reported a greater decrease of the WHR, suggesting a valuable modification of fat distribution pattern, especially at the abdominal level. It improves rates of ovulation, provides higher incidence of regular menstrual cycles and lower levels of total testosterone and fasting insulin **(Hanan et al., 2011)**.

Acupuncture is a treatment method used in Traditional Chinese Medicine (TCM). It has been used for treatment of neurological and musculoskeletal diseases such as intervertebral disk disease and spinal cord injury **(To and Wong, 2003)**.

In electro-acupuncture, the therapist inserts the acupuncture needles in acupuncture points and electric current is connected to the body through the acupuncture needles **(Ahsin et al., 2009)**. The stimulation can be measured more objectively and regulated more precisely through adjustments of the electrical current, amplitude and frequency. Electro-acupuncture can produce a higher and more continuous level of stimulation than manual manipulation; this is especially useful in acupuncture anesthesia. In addition, it is possible to apply the current through an electrode on the skin surface, without the aid of a needle inserted subcutaneously **(Steven and William, 2007)**.

Electroacupuncture promotes follicle development and corrects reproductive endocrine dysfunction in ovaries by regulating the functions of the hypothalamus, pituitary and ovaries **(Johansson et al., 2013)**.

Statement of the problem:

Is there is any difference between the effect of Ultrasound Cavitation and Elctroacupuncture on sex hormones in obese infertile patients with poly cystic ovarian syndrome?

Purpose of the study:

The aim of this study is to determine the difference between the effect of Ultrasound Cavitation and Electroacupuncture on sex hormones in obese infertile patients with poly cystic ovarian syndrome.

Significance of the study:

PCOS is the most common endocrine abnormality in reproductive-age women. The prevalence of PCOS is traditionally estimated at 4% to 8% from studies performed in Greece, Spain and the USA (**Arslanian et al., 2000**).

PCOS is the most common cause of an ovulatory infertility. It accounts for 90% to 95% of women attending infertility clinics with anovulation. However 60% of women with PCOS are fertile (defined as the ability to conceive within 12 months), although time to conceive is often increased. In those with PCOS and infertility, 90% are overweight. Obesity independently exacerbates infertility, reduces efficacy of infertility treatment and induces a greater risk of miscarriage (**Brassard et al., 2008**).

There is currently an active debate about the appropriate limit for body mass index for assisted reproduction therapies, given the reduced success rates and the demonstrated risks of pregnancy in overweight women. Ideally, weight should be optimized prior to pregnancy. Age-related infertility also exacerbates infertility and timely planning of families may warrant discussion (**Cedergren, 2007**).

Cavitation ultrasound is supposed to correct the negative impacts of abdominal adipose tissues on the ovarian function and clinical manifestations in women with PCOS and abdominal obesity (**Ascher, 2010**).

Many studies reported the efficacy and safety of cavitation in reducing visceral adipose tissues and abdominal subcutaneous tissue, and they showed that there is a great decrease in fat thickness of subcutaneous tissue within the treated area and there is consistent reduction in abdominal circumference >2 cm after a single treatment (**Jewell et al., 2012 and Saedi et al., 2013**).

Regarding the effect of electroacupuncture on infertile patient with PCO, previous clinical trials suggest that acupuncture may induce ovulation, improve menstrual frequency and improve depression, anxiety, and health-related quality of life in PCOS patients (**Stener-Victorin et al., 2013 and Zheng et al., 2013**). In addition, electroacupuncture is able to decrease abnormally high levels of circulating luteinizing hormone (LH), which affect the LH/follicle-stimulating hormone (FSH) ratio and high levels of testosterone (**Jedel et al., 2011**).

Till now, there are no previous studies that compare between the effect of ultrasound cavitation and electroacupuncture on sex hormones in obese infertile patients with PCO. So, this studies will be the first one in this issue. Therefore, this study will be of valuable benefits for medical services organizations and increase body of knowledge of physical therapists in scientific field.

Delimitations:

This study will be delimited to:

- 1- Forty obese infertile patients with poly cystic ovarian syndrome.
- 2- Their ages will be ranged between 20-35 year old.
- 3- Their body mass index will be ranged from 30-40 kg/m².
- 4- All of them are married women.

Limitations:

This study will be limited to the following criteria:

- 1- Psychological status.
- 2- Cooperation of the patients may affect the result of the study.
- 3- Environmental factors which may have affected the patient's response.
- 4- The daily effort may affect the result of the study.

Null Hypothesis:

It will be hypothesized that, there is no difference between the effect of ultrasound cavitation and electroacupuncture on sex hormones in obese infertile patients with poly cystic ovarian syndrome.

Basic assumptions:

It will be assumed that:

- 1- All patients will show adequate cooperation with study procedure.
- 2- All patients will follow the instructions that will be given to them.
- 3- Clinical methods of evaluation will be reliable and valid.
- 4- Results obtained from this study will be of value in physical therapy.

CHAPTER II

LITERATURE REVIEW

PCOS is the major endocrine disorder affecting females in age of reproduction and is considered to be the most common cause of an ovulatory infertility. According to diagnostic criteria, PCOS affects 12-21% of women in child bearing period of life; however, many cases are undiagnosed (**Stabile et al., 2014**). It represents a condition in which an estimate of 10 small cysts of a diameter ranging between 2 and 9 mm develop on one or both ovaries and/or the ovarian volume in at least one ovary exceeds 10 ml (**Balen and Rajkowha, 2003**).

Although it was previously considered as a disorder of adult women, recent evidence suggests that PCOS is a lifelong syndrome, manifesting since prenatal age. In fact, according to the Rotterdam diagnostic criteria, the prevalence of PCOS, in adolescents varies between a minimum of 3% (**Hashemipour et al., 2004**) and a maximum of 26% (**Driscoll, 2003**). However, the prevalence of the disease in children is still considered unknown (**Kamangar et al., 2015**).

The economic burden of PCOS is significantly huge. Around 4 billion dollars are spent annually in the United States to screen for the disease and treat its various morbidities, including hirsutism, infertility, and diabetes mellitus. The Australian Health System spends more than 800 million dollars every year to account for the disease (**Azziz et al., 2005**). Therefore, accurate and early diagnosis of PCOS is necessary not only to prevent future health comorbidities but also to reduce financial cost and burden (**Kamangar et al., 2015**).

Obesity and PCO

The prevalence of obesity reaches 80% in the United States and 50% outside which indicates that this figure depends on local environmental factors, ethnic backgrounds, and lifestyle, and not on the mere presence of PCOS itself. On the other hand, women with PCOS are at a higher risk of developing obesity **(Balen et al., 1995 and Randeve et al., 2012)**.

Many studies explain that females with PCOS have increased visceral and subcutaneous body fat distribution due to increased androgen production rates; this central obesity follows a masculinized body fat distribution where the amount of visceral fat correlates with the degree of insulin resistance **(Karabulut et al., 2012 and Borrueal et al., 2013)**.

Obese women with PCOS have a characteristic distribution of a central pattern of body fat known as android obesity in which fat deposited in the abdominal wall and visceral mesenteric area. This fat is more sensitive to catechol-amines and less sensitive to insulin **(Pasquali and Casimirri, 2003)**. In addition, women with higher waist/hip ratios (i.e. more abdominal relative to hip fat) have higher total androgen and lower SHBG levels **(Pasquali et al., 1997)**.

Moreover, obesity plays a significant role in expressing the metabolic features of PCOS. Women with PCOS have an atherogenic lipid profile, associated with elevated levels of low-density lipoprotein, triglycerides and cholesterol, along with decreased levels of high-density lipoprotein. They are also at a higher risk of developing atherosclerosis, arterial stiffness, and altered vascular endothelium **(Hart and Norman, 2006)**. In addition, women with PCOS show a worsened cardiovascular profile and associated complications **(Randeve et al., 2012)**.

However, obesity by itself is not the main reason behind these features. This is evident in lean women with PCOS who demonstrate the same metabolic features as those who are obese (**Balen et al., 1995**). Whether obesity leads to PCOS or whether PCOS leads to obesity is still debatable (**Kamangar et al., 2015**).

Obesity is also seen and associated with insulin resistance and decreased SHBG as well as, in many cases, increased testosterone concentrations (**Velazquez, 2006**). Thus, obesity appears to be strongly related to affect the activity of hypothalamic-pituitary axis which causes excessive LH concentrations resulting in a lower chance of conception (**Regan et al., 2005**).

Infertility and PCO:

Women with PCOS may have reduced fertility due to the associated endocrine and gynecologic abnormalities that impact ovarian quality and function (**Hart and Norman, 2006**). Accounting for up to 90% of ovulatory disorders, PCOS associated persistent periods of anovulation are positively correlated with infertility (**Imani et al., 1998**).

In 1995, a study reported up to 50 and 25% of women in a PCOS population suffering from primary and secondary infertility respectively (**Balen et al., 1995**). On the other hand, some studies suggested that females with PCOS who conceive might suffer from pregnancy-related complications such as gestational diabetes, pregnancy induced hypertension and preeclampsia to a higher extent in comparison to matched controls (**Sir-Petermann et al., 2012; Bruyneel et al., 2014 and Katulski et al., 2015**).

Various research data also suggest an increased risk of miscarriage in women with PCOS (**Winter et al., 2002**). Concerning the effects on

the embryo, women with PCOS are 2.5 times at a higher risk of giving birth to small for gestational age children in comparison to healthy females (**Katulski et al., 2015**) and offspring show an increased morbidity and mortality compared to control (**Fauser et al., 2012**).

Various methods used in the treatment of PCO:

Therapeutic strategies in PCOS include diet-induced weight loss, exercise and medical therapy fail to optimally treat PCOS and all of these can reduce but not reverse IR (**Sabbour et al., 2009**).

1- Hypocaloric diet :

Standard dietary management of obesity and related comorbidities is a nutritionally adequate, low fat (approximately 30% of energy, saturated fat approximately 10%), moderate protein (approximately 15%) and high carbohydrate intake (approximately 55%), with increased fiber-rich wholegrain breads, cereals, fruits and vegetables and moderate regular exercise. A moderate energy reduction diet (500 to 1,000 kcal/day reduction) reduces body weight by 7% to 10% over a period of 6 to 12 months (**Dansinger et al., 2005**).

2- Life style modification:

Lifestyle change is first line treatment in an evidence-based approach in the management of the majority of PCOS women who are overweight (**Moran et al., 2009**).

Furthermore, prevention of excess weight gain should be emphasized in all women with PCOS of both normal or increased body weight. As little as 5% to 10% weight loss has significant clinical benefits improving psychological outcomes, reproductive features (menstrual cycle, ovulation and fertility) and metabolic features (insulin resistance and risk factors for CVD and DM2) (**Galletly et al., 1996**). Evidence

shows that lifestyle change with small achievable goals results in clinical benefits even when women remain in the overweight or obese range **(Wahrenberg et al., 1999)**.

3- Exercise:

Incorporating simple moderate physical activity including structured exercise (at least 30 min/day) and incidental exercise increases weight loss and improves clinical outcomes in PCOS compared to diet alone. Exercise alone also improves clinical outcomes **(Poehlman et al., 2000)**.

Aerobic exercise for 12 weeks is an effective method to decrease visceral fat, waist circumference, in obese subjects with T2DM even without weight loss. Frequent aerobic exercise has been shown to increase HDL-C levels by approximately 5% as early as 2 months from start of regular exercise in sedentary but otherwise healthy individuals **(Dekker et al., 2007)**.

4- Medical treatment:

A- Oral contraceptive pills (OCP):

OCP are the most commonly used medications for the long-term treatment of women with PCO and have been recommended by the Task Force and the Endocrine Society **(Legro et al., 2013)**, the Australian Alliance **(Misso et al., 2014)** and the PCOS Consensus Group as first-line treatment for hyperandrogenism and menstrual cycle irregularities in women with PCOS **(Fauser et al., 2012)**.

By suppressing the hypothalamic-pituitary-ovarian axis, OCP decrease LH secretions, increase sex hormone binding globulins, and decrease free testosterone levels. This addresses hyperandrogenism-mediated symptoms improving acne and hirsutism, corrects menstrual

cycle abnormalities and provides a mean for effective contraception **(Costello et al., 2007)**.

Even though guidelines do not specify the use of one OCP over another and the best choice for symptomatic treatment is considered to be low-dose oral contraceptives that contain anti-androgenic or neutral progestin **(Fauser et al., 2012 and Legro et al., 2013)**.

A number of clinical trials encouraged the use of OCP in patients with PCOS with increased risk of insulin resistance **(Baillargeon et al., 2003 and Legro et al., 2013)**. Concerns have been also raised about the negative effects of OCP on the cardiovascular profile of females with PCOS **(Baillargeon et al., 2005)**.

B- Metformin:

Metformin (Glucophage), an oral anti-diabetic biguanide drug, acts by impeding hepatic glucose production and increasing the peripheral insulin sensitivity **(Bailey and Turner, 1996)**. Some data revealed that metformin does not improve insulin resistance itself, rather it improves glucose effectiveness, i.e., the ability of glucose per se to repress endogenous glucose synthesis and stimulate glucose uptake **(Pau et al., 2014)**.

Metformin treatment of obese adolescents with PCOS and impaired glucose tolerance proved beneficial in improving glucose tolerance and insulin sensitivity, in lowering insulinemia and in reducing elevated androgen levels **(Arslanian et al., 2002)**.

Even though studies show contradictory results regarding metformin effect, it is suggested as first-line treatment for cutaneous manifestations and pregnancy complications in women with PCOS. It is also used as a combination with clomiphene citrate to improve fertility

outcomes in clomiphene citrate resistant patients (**Legro et al., 2013 and Misso et al., 2014**).

5- Ultrasound cavitation:

Ultrasound Fat Cavitation (USFC) is the method in handling obesity, especially in destroying fat and shaping a particular part of the body. As one of the non-surgical correction methods, USFC is preferred at decreasing the risk of complications due to obesity (**Palumbo et al., 2011**).

The cavitation used in the field of aesthetic medicine is an innovative technique for a nonsurgical reduction of the localized fat and cellulite, Ultrasonic vibrations spread in the form of a wave in medium such as a liquid or a solid. When the particles of an elastic medium are under ultrasonic vibration, they act continuously in only one direction (**Sabbour et al., 2009**).

This phenomenon called cavitation is a very smart way to reduce fat because it is converting the fat into liquid and then is naturally eliminated with the urine when cavitation therapy is followed by lymphatic drainage. The process is faster and the drainage is very effective (**Ter-Haar and Coussios, 2007**).

Studies have proven that ultrasound is characterized as a safe, noninvasive, reliable and predictable ways for body sculpting (**Palumbo et al., 2011**). Despite that, a lot studies claim to produce statistically significant results, the clinical benefits of ultrasound have yet to be approved (**Ascher, 2010**). This reduction in regional fat distribution could contribute to the effect of cavitation in improving the hormonal profiles (higher rates of ovulation, higher rate of regular menstrual cycles, lower

levels of LH/FSH Ratio and total testosterone) in obese women with PCOS (**Hanan et al., 2011**).

6- Electroacupuncture:

Acupuncture has been the subject of active scientific research since the late 20th century but it remains controversial among medical researchers and clinicians. It is able to decrease abnormally high levels of circulating luteinizing hormone (LH), which affect the LH/follicle-stimulating hormone (FSH) ratio and high levels of testosterone (**Ernst et al., 2007**).

Point selection, location and application:

There are tender areas at certain points of the body surface with all diseases, regardless of whether they are physical or mental, which disappear when the illness is cured. There are called acupuncture points. **Jayasuria (1993)**, stated that the use of acupuncture points to treat diseases of local and adjacent areas is one of the key principles in the practice of acupuncture therapy. It is the first consideration that should govern the selection of the acupuncture points for any regional disease. The local points are the most effective points in treating a majority of disorders. Every acupuncture point has a local effect on the surrounding tissues (**Stux and Pomeranz, 1998**).

Location methods for body acupuncture :

- 3- Concomitant cardiovascular disorders.
- 4- Respiratory, renal and liver dysfunction.
- 5- Tubal adhesions as well as uterine abnormalities.

All patients will be divided randomly into two equal groups (A&B).

Group A:

It will consist of twenty obese infertile patients with PCO who will be treated by ultrasound cavitation on the abdomen, 2 times per week for 3 months with medical treatment in addition to hypocaloric diet (1200 kcal/day) for 3 months.

Group B:

It will consist of twenty obese infertile patients with PCO who will be treated by electroacupuncture, 3 times per week for 3 months with medical treatment in addition to hypocaloric diet (1200 kcal/day) for 3 months.

All patients will be given a full explanation of the study protocol and consent form will be signed by each woman before participating in the study, the purpose and nature of the study will be explained to all patients (**Appendix I**).

II- Instrumentations:

1- Recording data sheet (Appendix II).

2- Standard weight height scale:

It will be used to measure weight and height to calculate the body mass index (BMI) for each woman.

3- Tape measurement:

It will be used to calculate the waist/hip ratio.

4- Test tubes:

Sterilized test tubes will be used to collect the blood samples from obese infertile patients with PCO.

5- Kites:

They will be used for assessment of serum progesterone level, testosterone, LH and FSH hormones.

6- Abdominal ultrasonography:

It will be used for measuring ovulation rate.

7- Focused ultrasound cavitation:

Fat cavitation, biCAVI (Ultimate). It will be used to apply the treatment procedure for all patients in group A.

8- Electro acupuncture:

It will be used to apply the treatment procedure for all patients in group B.

III- Procedures:

A-Evaluative procedures:

1. Weight and height measurements:

Weight and height measurements will be measured while the patient is wearing a thin layer of clothes to calculate the BMI according to the following equation before and after treatment for both groups (A&B):

$$\text{BMI} = \text{weight/height}^2 \text{ (kg/m}^2\text{)}.$$

2. Waist and Hip Ratio:

- It must be taken in order to accurately measure obesity rather than just visually inspecting of naked body (reference of female measurements : minimal waist circumference >88 cm and waist-hip ratio >0.85).
- It is measured by tape, waist Circumference will be measured at the narrowest portion of the torso approximately midway between the lower costal margin and the iliac crest and the hip circumference will be measured over the widest portion of the gluteal and greater trochanteric region then the ratio between them will be calculated.

3. Blood analysis:

Blood samples will be drawn from antecubital vein of each patient before and after treatment. It will be centrifuged within 2 hours after withdrawal. Serum is stored at -20 °C and assayed for LH/ FSH Ratio, Testosterone and Luteal Serum Progesterone. They will be measured from 3th day from menstrual cycle (**Richard et al., 2010 and Ellaithy, 2012**).

4. Ovulation rate:

- It will be done before and after treatment for patients in both groups through luteal serum progesterone assay.
- The number of patients who had evidence of successful ovulation during the 3 months.
- Ovulation will be confirmed by the elevation of serum progesterone level.

B- Treatment procedures:

1- Medical treatment:

Both group (A&B) will follow the same medical treatment as prescribed by gynecologist.

2- Hypocaloric diet:

Both group (A&B) will follow the same hypocaloric diet as prescribed by nutrition specialist (1200kcal per day).

3- Ultrasound cavitation:

- Each patient in group A will be treated by ultrasound cavitation, two sessions per week for 3 months.

- Before starting treatment session, each patient will be instructed to evacuate her bladder to make sure that she is comfortable and relaxed throughout the treatment session.
- From standing position, the abdominal area of each patient will be divided transversally into 3 parts; Part I: from the xiphoid process to 3 cm above the umbilicus, Part II: from 3cm above the umbilicus to 2 cm below the umbilicus and Part III: from 2 cm below the umbilicus to the pubic bone, and vertically each part was divided into right and left segments in relation to the linea alba, forming a total of 6 abdominal segments.
- Skin of the anterior abdominal wall will be cleaned with alcohol then, a conducting medium (gel) will be applied to the cavitation head of the ultrasound device, the device will be turned on, the program of cavitation; frequency (40 kHz) will be chosen, the time will be adjusted at 30 minutes and the intensity will be adjusted at 50% in the first 6 sessions while it will be adjusted at 75% at the last 6 sessions.
- Then the cavitation head will be moved very slowly on each abdominal segment in a small circular movement for 5 minutes.
- After finishing the focused ultrasound of the 6 segments of the abdomen, the skin will be cleaned with cotton. The total duration of the ultrasound treatment session on the 6 segments of the abdominal area will be 30 minutes.

4- Electroacupuncture:

- Each patient in group B will be treated by electroacupuncture, three sessions per week for 3 months.
- The electrodes must be applied on the effective acupuncture points in somatic segments that innervates the ovary and uterus (Th12-L2 and S2-4).

- Electric stimulation with low frequency 2Hz, pulse width 0.5ms for 30minutes will be chosen.

Statistical analysis:

Data will be collected and statistically analyzed using:

- Descriptive statistics including mean and stander deviation.
- Unpaired t-test will be conducted for comparison of mean values of pre and post-treatment between groups.
- Paired t-test will be conducted for comparison between pre and post-treatment mean values in each group.
- Level of significance, the degree of significance will be selected at 5%, P value <0.05 will indicate non-significant results, P value > 0.05 will indicate a highly significant result.

REFERENCES

Ascher B. 2010: Safety and efficacy of ultra-shape contour I treatments to improve the appearance of body contours. : Multiple treatments in shorter intervals. *A.S.J.*, 30 (2): 217-24.

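### The cycle day for luteal progesterone is either contradicted or left unfixed, and the three-month ovulation count has no stated data source

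*Protocol*

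**What the plan says.** All of this is in the protocol; no SAP was available.

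- **Sampling times** (Chapter III, Evaluative procedures, item 3, Blood analysis): "Blood samples will be drawn from antecubital vein of each patient before and after treatment".
- **Assays** (same item): the serum is "assayed for LH/ FSH Ratio, Testosterone and Luteal Serum Progesterone".
- **Cycle day** (the next sentence): "They will be measured from 3th day from menstrual cycle".
- **Ovulation rate, timing and method** (item 4): "It will be done before and after treatment for patients in both groups through luteal serum progesterone assay".
- **Ovulation rate, definition** (item 4): "The number of patients who had evidence of successful ovulation during the 3 months".
- **Ovulation rate, criterion** (item 4): "Ovulation will be confirmed by the elevation of serum progesterone level". No level is given there. The only level in the protocol, mid-luteal progesterone above 6 ng/ml, is in Chapter II under Sex hormones changes.
- **Instruments** (Chapter III, Instrumentations): of the assay kits, "They will be used for assessment of serum progesterone level, testosterone, LH and FSH hormones"; of abdominal ultrasonography, "It will be used for measuring ovulation rate".
- **Recording sheet** (Appendix II): a progesterone row with one cell before and one after treatment. As shown, it has no field for cycle day, ovulation or ultrasonography.
- **Analysis** (Statistical analysis): means are compared by unpaired t-test between groups and by paired t-test within each group.

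**The concern.** Two things fixed in the protocol do not fit together.

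**Timing.** The pronoun in the cycle-day sentence takes in every assay just listed, including the luteal one. Staff who follow the text have no workable instruction for progesterone: either it contradicts the word luteal, or it gives only a starting day. Progesterone is one of the three hormone rows on the recording sheet, and the stated aim concerns sex hormones, so the defect reaches the aim. It is also a sampling matter. A later analysis plan can add a cut-off, but it cannot supply a luteal sample that was not taken.

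**Window.** A count of women who ovulated at any time in three months needs information from across those months. The stated blood samples are one before and one after treatment, and no other source is scheduled. As written, a reader of the results could not tell what period the ovulation rate describes.

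**Working it through.** The protocol gives no ovulation rate, number of cycles or progesterone values, so there is no figure to reproduce and no effect size to compute. The check sets the texts side by side and adds simple counts.

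**Step 1: the two readings of the cycle-day sentence.**

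| Reading | Fit with a luteal assay | Fit with the mid-luteal criterion (above 6 ng/ml) | Result |
|---|---|---|---|
| On day 3 | Conflicts | Cannot be applied | Progesterone sample is not luteal |
| Day 3 onwards | Compatible | Applies only if the draw happens to be mid-luteal | Luteal day not fixed |

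Neither reading yields a defined luteal sample. The LH/FSH ratio and testosterone are compatible with the sentence; only progesterone is affected.

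**Step 2: what an unfixed day does to the mean.** Chapter II describes persistent anovulation (Infertility and PCO) and menstrual irregularity (Medical treatment) in this condition, so the luteal phase cannot be assumed to fall on a known day. Let a share π of the samples be luteal, and let d be the difference between the luteal and non-luteal means. Pooling them adds π(1 − π)d² to the variance of progesterone. The documents give neither π nor d, so the term cannot be evaluated. Both groups share the same sampling text, and nothing in the documents makes π differ between them. The supportable consequence is added noise, not a shift in favour of one arm. The Statistical analysis section does not name its variables; I take progesterone to be among them because it is a recorded hormone.

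**Step 3: the ovulation window.**

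- Progesterone results per woman: 1 before + 1 after = 2.
- In the trial: 2 × 40 = 80.
- After treatment: 1 × 40 = 40, one per woman.

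The first result precedes the three months. The second informs on one occasion. Together they do not give a count over three months.

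**Step 4: could ultrasonography fill the gap?** Instrumentations names it for ovulation rate. The Ovulation rate item does not mention it, and gives it no schedule, criterion or rule for combining it with progesterone. The protocol therefore neither provides scans during the three months nor excludes them. What can be said is that the three-month count has no stated data source.

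**The case against.** **Luteal already fixes the timing.** The procedures use the word twice, and Chapter II ties progesterone to a mid-luteal sample. The day-3 sentence carries two citations: one is also the source of the mid-luteal criterion, and the other, by its title in the reference list, is about testosterone assays. This stands as far as it goes. It makes a literal day-3 progesterone draw the less plausible reading, and a reader who infers that progesterone will be drawn on day 3 and so cannot show ovulation goes further than the text. It does not rescue the sentence, because the likelier reading still states no luteal day.

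**Ultrasonography may supply the three-month count.** It may, and so the documents do not support saying that the reported rate will be a single-occasion result labelled as a three-month one. The gap is that the protocol does not say where the count comes from.

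**Both arms are sampled alike.** This stands too. A reader might infer a biased comparison, but the documents show none.

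**The recording sheet may not be the only record.** Correct. The absence of a cycle-day field on the sheet as shown does not prove that the day could never be recovered; it means only that the protocol does not ask for it.

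**The SAP can settle it.** It could carry the 6 ng/ml cut-off into the outcome definition, and the absence of that figure from Chapter III is a minor matter. It cannot change when blood was drawn.

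**Conclusion.** The point holds in a limited form and should be corrected before sampling begins. The cycle-day sentence either contradicts a luteal sample or, more plausibly, leaves its day unfixed, so progesterone, one of three recorded hormones, would mix luteal and non-luteal values. Separately, the three-month ovulation count does not match the before-and-after assessment and has no stated data source.

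The timing part carries more weight, because it reaches the stated aim; ovulation rate is not itself that aim. In size, the stated sampling yields one post-treatment progesterone result per woman, 40 in all. The conclusion assumes that the stated blood draws are the only ones planned, which the text and the two-column recording sheet suggest but do not say outright, and that progesterone is among the variables compared by t-test.

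**What to change.** 1. **Blood analysis (item 3).** Replace the single cycle-day sentence with a separate time for each assay: keep the day-3 statement for LH, FSH and testosterone, and state a mid-luteal time for progesterone. Record the cycle day of every sample, for example as an added field in Appendix II.
2. **Ovulation rate (item 4).** Reconcile the window with the sampling, in one of two ways:
   - Report the proportion of women ovulating in the assessed cycle, before and after treatment, by the protocol's own criterion of mid-luteal progesterone above 6 ng/ml, and drop the three-month wording.
   - If a three-month count is meant, keep it and state the data source and schedule that supply it.
3. **Ultrasonography (Instrumentations, item 6).** State whether it contributes to ovulation rate, so that this entry and the Ovulation rate item agree.

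**Cost.** Mainly wording and one cycle-day field. With the first option in item 2, the ovulation claim narrows to one cycle at each time. If a single draw per assessment was intended, one further luteal draw is needed at each: 1 × 2 assessments = 2 per woman, and 2 × 40 = 80 in the trial. If separately timed luteal draws were already intended, these are not extra. The cost of keeping a three-month count depends on the source chosen and cannot be derived from the protocol.
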